### 13.2.2 Interim Safety and Futility Analyses

One interim safety analysis will be performed in this study when 12 patients are evaluable for toxicity at pre-C4 (week 10) of the study. If at that time, 4 or more patients have experienced unexpected study drug related serious adverse events (SAEs), we will conclude that the combination immunotherapy regimen is too toxic and accrual will stop.

The properties of interim safety stopping rules are given in the table below.

True Probability of Study Drug-Related SAEs (ptox)	Probability of Stopping Early
0.10	0.026
0.14	0.075
0.18	0.155
0.22	0.261
0.26	0.382
0.30	0.507

One interim futility analysis will be performed in this study. A Simon 2-stage design will be used: Twelve patients will be enrolled initially. If 0 respond the study will be stopped for futility. The probabilities of stopping the trial for futility at this interim analysis are 54% and 3% under the null hypothesis (ORR=5%) and alternative hypothesis (ORR=25%) respectively.

Otherwise an additional four patients will be enrolled. If three or more out of 16 patients respond, the treatment will be considered promising and would likely lead to widespread use of this regimen in the clinic.

The overall type I error for the study is 4.3%, and the overall power of the study at the alternative hypothesis (ORR=25%) is 80.1%.

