## SCHEMA

Title	A Phase II Trial of MK-3475 (pembrolizumab) and Interferon Gamma 1-b Combination Immunotherapy in Patients with Previously Treated Mycosis Fungoides and Sézary Syndrome (Treatment Group 1) and in patients with Advanced Synovial Sarcoma (Treatment Group 2)
Trial Phase	Phase II
Clinical Indication	Treatment Group 1: Stage IB-IVB Mycosis Fungoides/Sézary Syndrome, and who have relapsed, are refractory, or progressed after at least one standard systemic therapy  Treatment Group 2: Translocation associated sarcoma that generally expresses NY-ESO-1 (e.g. Synovial Sarcoma or Myxoid/Round Cell Liposarcoma). Patient must have metastatic or unresectable disease.
Trial Type	Nonrandomized, open-label, phase II, interventional study
Type of control	None
Route of administration	Intravenous (IV) for MK-3475 (pembrolizumab), Subcutaneous for Interferon-Gamma
Trial Blinding	None
Treatment Groups	Treatment Group 1: Patients with Mycosis Fungoides and Sézary Syndrome: MK-3475 (pembrolizumab), 200 mg every 3 weeks in combination with Interferon Gamma-1b (ACTIMMUNE®), 50 mcg/m  three times per week.  Treatment Group 2: Patients with advanced synovial sarcoma: MK-3475 (pembrolizumab), 200 mg every 3 weeks [2 mg/kg (max= 200 mg) in patients under 18 years of age] in combination with Interferon Gamma-1b (ACTIMMUNE®), 100 mcg/m  once per week.
Number of trial subjects	Treatment Group 1: Mycosis Fungoides and Sézary Syndrome (n=30) Treatment Group 2: Synovial Sarcoma (n=16)
Estimated duration of trial	3 years
Duration of Participation	Patients may receive study directed therapy for up to 2 years if they continue to respond.

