Toxicity will be assessed by CTCAE v. 5.0. Although interferon gamma-1b in combination with MK-3475 (pembrolizumab) has previously been seen to be safe, its side effect profile has not been confirmed in a synovial sarcoma patient population or in a population of patients with cold tumors. There is no reason to suspect there would be additional toxicity in these patients however, we will adopt CTEP's data safety monitoring plan of every two week teleconferences attended by all participating site principal investigators, CTEP staff and CITN Coordinating Center staff to oversee the safety of the trial. During each activated protocol teleconference all patient toxicities, including all serious adverse events (SAE) and all other clinical data will be reviewed. Any SAE suspected to be attributed to the study regimen will be distributed to all participating site principal investigators and their staff on an urgent basis. If necessary, an ad hoc teleconference may be convened to discuss any adverse event determined to be a patient safety issue or if the adverse event is suspected of being related to study treatment.

Radiographic assessment by CT scan will occur every 12 weeks. Response and progression will be determined using RECIST v1.1. All patients with either a CR, PR or stable disease (SD) will continue therapy for up to two years. Patients will be followed for up to two years after study discontinuation for disease status and survival. Patients with radiographic progression but who are otherwise stable without symptomatic progression may continue treatment up until confirmation at the next radiographic imaging time point in order to assess for possible pseudo progression. ORR based on immune related response criteria (IRRC) will also be noted as an exploratory endpoint.

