#### Summary of Interim Safety and Futility Analyses Strategy

Key Endpoints for Interim Analysis	Timing of Interim Analysis	Purpose of Interim Analysis
Study drug related serious adverse events (SAEs)	12 subjects enrolled and received at least 1 dose of either IFN-g or MK-3475 (pembrolizumab), with 12th pt evaluable through interim safety assessment time point at pre-C4/week 10	Stop for significant safety concerns. Enrollment will not stop in order to wait for the 12th patient to reach week 10. New patient enrollment will continue as long as there are less than 4 study drug-related SAEs.
Overall response rate (ORR) per global assessment of Mycosis Fungoides and Sézary Syndrome (confirmed & investigator assessed)	12 subjects enrolled and received at least 1 dose of either IFN-g or MK-3475 (pembrolizumab); all 12 subjects followed for 6 months	Stop for futility of combination therapy relative to monotherapy.

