#### 13.2.4 Sample Size and Power

A Simon 2-stage design will be used: Twelve patients will be enrolled initially. If 0 respond the study will be stopped for futility. The probabilities of stopping the trial for futility at this interim analysis are 54% and 3% under the null hypothesis (ORR=5%) and alternative hypothesis (ORR=25%) respectively.

Otherwise, an additional four patients will be enrolled. If three or more out of 16 patients respond, the treatment will be considered promising and would likely lead to widespread use of this regimen in the clinic. The overall type I error for the study is 4.3%, and the overall power of the study at the alternative hypothesis (ORR=25%) is 80.1%.

The patient demographics for the addendum is expected to be similar to the patient demographics of the original protocol. The planned enrollment report is given below.

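### Group 2's only numeric safety stopping rule is a single look after 12 of at most 16 patients, so the rule itself can spare at most four; a running count would act earlier at no statistical cost

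*Combined protocol and SAP*

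**What the plan says.** Section 13.2.2 sets one safety look for Group 2: "One interim safety analysis will be performed in this study when 12 patients are evaluable for toxicity at pre-C4 (week 10) of the study". The count is judged at that moment: "If at that time, 4 or more patients have experienced unexpected study drug related serious adverse events (SAEs"), in which case the regimen is declared too toxic and accrual stops.

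The same section gives the Simon design: "Twelve patients will be enrolled initially. If 0 respond the study will be stopped for futility". If there is a response, "Otherwise an additional four patients will be enrolled". Section 13.2.4 repeats this, and the Schema gives a maximum of 16.

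For Group 1, the table summarising the interim analyses in 13.1.1.4 adds a running condition: "New patient enrollment will continue as long as there are less than 4 study drug-related SAEs". Section 13.2 has no counterpart for Group 2.

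Section 5.2.2 describes the other Group 2 oversight. Teleconferences every two weeks review all toxicities and SAEs, suspected related SAEs are circulated urgently, and "If necessary, an ad hoc teleconference may be convened to discuss any adverse event determined to be a patient safety issue". No count or required action is attached. Section 5.4 lists sponsor termination, and 7.3.3 sets expedited SAE reporting timelines.

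**The concern.** By the time the Group 2 rule can act, 12 of 16 patients (75%) have been enrolled and the twelfth has reached week 10. Read literally, if the first four patients all had qualifying events, the written rule would not stop patients 5 to 12 from enrolling. The look at 12 leaves 18 of 30 patients still to enrol in Group 1, but only 4 of 16 in Group 2. The group in which a single look can achieve least is therefore the one without the running condition.

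Section 5.2.2 itself says that the combination's side-effect profile is unconfirmed in this population. Group 2 also admits patients from age 12 and with ECOG 2 (3.1.2), whereas Group 1 requires age 18 or over and ECOG 0 or 1 (3.1.1). At stake is how many patients are exposed if the regimen proves toxic. The response analysis is not in question.

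**Working it through.** **Inputs.** Threshold 4 of 12, judged once at week 10 (13.2.2); 12 patients then 4 (13.2.2, 13.2.4); maximum 16 (Schema); printed stopping table for true rates p from 0.10 to 0.30 (13.2.2).

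**1. Reproduce the printed table.** P(stop) = P(X ≥ 4), with X binomial (12, p). For p = 0.10, 0.14, 0.18, 0.22, 0.26 and 0.30 this gives 0.026, 0.075, 0.155, 0.261, 0.382 and 0.507. All six match. The Simon figures also reproduce: stage 1 stopping 54.0% and 3.2%, type I error 4.27%, power 80.1%.

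**2. The most the single look can spare.** 16 − 12 = 4. This is an upper limit:
- Nothing in 13.2.2 holds stage 2 until patient 12 reaches week 10.
- If futility stops the group at 12 (54% when ORR is 5%), the safety rule spares nobody further.

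**3. The same threshold as a running count.** The fourth event falls at patient k with probability C(k−1, 3) p⁴ (1−p)^(k−4). Summing over k = 4 to 12 gives exactly P(X ≥ 4). The count cannot fall, so whether it reaches 4 within the first 12 does not depend on how often it is checked.

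**4. Patients saved among the first 12.** With immediate knowledge of events, the unconditional saving is P(stop) × (12 − mean k given triggering).

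| True rate p | P(stop) | Mean k if triggered | Saving |
|---|---|---|---|
| 0.10 | 0.026 | 10.1 | 0.05 |
| 0.18 | 0.155 | 9.7 | 0.35 |
| 0.30 | 0.507 | 9.1 | 1.5 |
| 0.50 (stress case) | 0.927 | 7.5 | 4.2 |

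For example, at 0.30: 0.507 × (12 − 9.08) = 1.48. The chance that the threshold is already met by patient 8 is 0.19 at 0.30 and 0.64 at 0.50.

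**5. Delayed knowledge.** The documents give no Group 2 accrual rate. Assume one patient per month and SAE onset uniform over 10 weeks. At p = 0.30, mean enrolment given triggering is then about 9.7 with fixed monthly accrual and about 10.0 with random (Poisson) accrual. The unconditional saving is 0.507 × (12 − 9.7) ≈ 1.2, or 0.507 × (12 − 10.0) ≈ 1.0.

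**6. Which event p refers to.** The rule counts unexpected related SAEs; the table's column heading is for all study-drug-related SAEs. The documents do not say what share is unexpected. Suppose that 75%, 50% or 25% of patients with a related SAE have an unexpected one. At a related-SAE rate of 0.30, the rate that the rule counts is then 0.225, 0.15 or 0.075, and P(stop) is 0.276, 0.092 or 0.010 instead of 0.507. The savings in step 4 likewise hold only when p is the rate of the event counted.

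**The case against.** The best case for the plan is that patients are not left unwatched until the twelfth reaches week 10. Investigators, CTEP and the coordinating center review all toxicities every two weeks. Grade 3 to 5 SAEs are reported within 24 hours, subject to the listed exceptions (7.3.3). The sponsor may terminate. Four early events would be seen well before the formal look. A reader might infer that patients 5 to 12 have no protection; the documents do not support that. What stands is that this protection is discretionary: no count obliges anyone to stop.

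A reader might also expect a large saving. The protocol's own evidence does not point to high rates: two related SAEs among 24 patients on pembrolizumab alone in another disease (2.4.3), and no related grade 3 or higher toxicity in five sarcoma patients on weekly interferon gamma (2.4.7). Neither is the combination in sarcoma, so high rates are not excluded, but 0.50 lies well beyond the printed table.

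The contrast with Group 1 should not be overdrawn. Its formal text (13.1.1.2, 13.1.1.4) is the same single look. The running condition is one summary-table sentence, worded in SAEs rather than patients. Group 2's omission may be a drafting gap, since 13.2.4 calls this group an addendum. That explains the difference but does not remove it.

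Finally, a single look at the Simon stage boundary is a recognisable choice in a 16-patient group. But a running count has the same stopping probability and uses data already reviewed at the calls, so the single look has no statistical advantage.

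**Conclusion.** The point holds for the formal rule. Group 2's only numeric safety boundary acts after 12 of at most 16 patients and can spare at most four. The same threshold applied continuously would stop in exactly the same cases, but sooner.

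The expected gain is small at low rates and moderate at the top of the printed range: about 0.05 patients at 0.10, 0.35 at 0.18 and 1.5 at 0.30 with immediate knowledge of events. At 0.30 it is about 1.0 to 1.2 under the assumed accrual of one patient per month. These figures assume independent patients, a common rate, and that p is the rate of the event the rule counts.

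This is not a calculation error: the printed probabilities are correct binomial values for 4 of 12. They describe the written rule only if p is the rate of unexpected related SAEs, which is not how the table is labelled.

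**What to change.** In 13.2.2, replace the single look with wording such as: accrual to Group 2 stops as soon as a fourth patient among the first 12 meets the criterion through pre-C4 (week 10), with the count of patients updated at each two-week teleconference. Keep the threshold and window, and add that continuous counting does not change the stopping probabilities.

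Separately, reconcile the event named in the rule with the event named in the table heading, and state which one p describes.

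The cost is a sentence or two. No extra patients are needed, the Simon design is unchanged, and the calls already review the SAE data. The downside is that accrual may stop earlier with fewer response-evaluable patients, but only in cases where the existing rule would have stopped accrual anyway.

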### 5.2.2 Synovial Sarcoma (Treatment Group 2)

The study is a single arm, open label trial of interferon gamma-1b and MK-3475 (pembrolizumab) for patients with advanced (unresectable or metastatic) synovial sarcoma. Both adult and pediatric patients are eligible to participate in this trial. Patients will receive interferon gamma-1b at a dose of 100 mcg/m^2 weekly, as this dose has been found to be relatively well tolerated and successful at inducing MHC expression and T cell infiltration into synovial sarcoma tumors. Interferon gamma-1b will begin one week prior to initiating MK-3475 (pembrolizumab). MK-3475 (pembrolizumab) will be given at a standard fixed dose of 200 mg administered every 3 weeks. Thus patients will receive one dose of interferon gamma-1b priming their tumors for checkpoint blockade using MK-3475 (pembrolizumab). If substantial toxicity occurs, interferon gamma-1b, but not MK-3475 (pembrolizumab), will be dose de-escalated.

The primary endpoint of the study will be the overall response rate (ORR) based on RECIST v. 1.1. The ORR is defined as the complete response rate (CR) combined with the partial response rate (PR). Based on historical controls, we estimate the ORR of single agent pembrolizumab is less than 5%. Twelve patients will be enrolled initially. If one or more of these patients respond, an additional four patients will be enrolled. If three or more patients respond the treatment will be considered promising.

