#### 7.1 Comprehensive Adverse Events and Potential Risks List(s) (CAEPRs)

The Comprehensive Adverse Event and Potential Risks list (CAEPR) provides a single list of reported and/or potential adverse events (AE) associated with an agent using a uniform presentation of events by body system. In addition to the comprehensive list, a subset of AEs, the Specific Protocol Exceptions to Expedited Reporting (SPEER), appears in a separate column and is identified with bold and italicized text. The SPEER is a list of events that are protocol-specific exceptions to expedited reporting to NCI (except as noted below). Refer to the 'CTEP, NCI Guidelines: Adverse Event Reporting Requirements'

[http://ctep.cancer.gov/protocolDevelopment/adverse\\_effects.htm](http://ctep.cancer.gov/protocolDevelopment/adverse_effects.htm) for further clarification.

**NOTE:** Report AEs on the SPEER **ONLY IF** they exceed the grade noted in parentheses next to the AE in the SPEER. If this CAEPR is part of a combination protocol using multiple investigational agents and has an AE listed on different SPEERs, use the lower of the grades to determine if expedited reporting is required.

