#### 13.1.1.4 *Interim Safety and Futility Analyses*

- One interim safety analysis will be performed in this study when 12 patients are evaluable for toxicity at pre-C4 (week 10) of the study. If at that time, 4 or more patients have experienced study drug related serious adverse events (SAEs), we will conclude that the combination immunotherapy regimen is too toxic and accrual will stop.
- The properties of interim safety stopping rule are given in the table below.

True Probability of Study Drug Related SAEs (ptox)	Probability of Stopping Early (pstope)
0.10	0.026
0.14	0.075
0.18	0.155
0.22	0.261
0.26	0.382
0.30	0.507

One interim futility analysis will be performed in this study. Results will be reviewed by the participating institutions/investigators, CITN, NCI/CTEP, and participating industry sponsors (Horizon and Merck).

The statistical criterion for success requires ORR that is greater than 37% (null) and at least 65% (alternative). This is a single stage trial. Patients will be recruited continuously. We will perform the interim futility analysis when 12 patients have been followed for 6 months. If ORR is less than 33% (4 or less CR+PR), the trial will stop and we will accept the null that combination therapy is no better than monotherapy. The probability of

stopping at interim futility analysis under the null and alternative are 52% and 2% respectively.

Otherwise, the trial will continue until we reach 30 patients. If ORR is at least 57% (17 or more CR+PR) at the final analysis, we will accept the alternative that combination therapy is significantly better than monotherapy. The type I error rate is 2%. The power is 87%.

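### The Group 2 safety rule counts only unexpected drug-related SAEs (a term left undefined), but its stopping table is headed by all drug-related SAEs, so under that heading the printed probabilities are upper bounds

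*Combined protocol and SAP*

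**What the plan says.** Section 13.2.2 plans one safety look in Group 2, when 12 patients are evaluable for toxicity before cycle 4 (week 10). Accrual stops if "4 or more patients have experienced unexpected study drug related serious adverse events (SAEs), we will conclude" that the combination is too toxic. The text then says: "The properties of interim safety stopping rules are given in the table below". The first column of that table is headed "True Probability of Study Drug-Related SAEs (ptox"), with values from 0.10 to 0.30. The second column gives stopping probabilities from 0.026 to 0.507.

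The Group 1 rule in section 13.1.1.4 has the same number of patients, threshold and timing, and the same six rows under essentially the same heading. Its trigger is "4 or more patients have experienced study drug related serious adverse events (SAEs"), with no restriction to unexpected events, so the Group 1 rule and table agree.

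Section 7.3.3 defines *serious* and section 7.2 defines attribution. Neither defines *unexpected*. Section 7.1 holds lists of known events, but describes the SPEER only by its reporting function: "The SPEER is a list of events that are protocol-specific exceptions to expedited reporting to NCI".

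**The concern.** The event that stops Group 2 is a subset of the event that indexes its table. A reader who takes the heading at face value would conclude that a true related-SAE rate of 30% stops accrual about half the time. The rule as written does not guarantee that.

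The count also needs a reference for *unexpected*, and the candidates can disagree. Diarrhea is on the pembrolizumab CAEPR in section 7.1.1.1, while its SPEER entry is limited to grade 2. A grade 3 diarrhea SAE is therefore listed on the first and above the limit of the second. Such an event is realistic: section 2.4.3 reports a related grade 3 diarrhea SAE in the pembrolizumab monotherapy trial. With a threshold of 4 in 12, the classification of one patient can decide the outcome.

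This is the only formal toxicity boundary in Group 2. Section 5.2.2 acknowledges that the side-effect profile of the combination is not yet confirmed in these patients.

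**Working it through.** **Inputs.** From section 13.2.2: n = 12, stop at 4 or more, ptox = 0.10 to 0.30; futility stop if 0 of 12 respond, with ORR 5% (null) and 25% (alternative); four further patients otherwise. The documents do not give *f*, the share of patients with a related SAE who have an unexpected one. The values 1, 0.75 and 0.50 below are assumptions.

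**Step 1: reproduce the table.** The formula is P(X ≥ 4) with X ~ Binomial(12, ptox).

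| ptox | Printed | Recomputed |
|---|---|---|
| 0.10 | 0.026 | 0.0256 |
| 0.14 | 0.075 | 0.0750 |
| 0.18 | 0.155 | 0.1552 |
| 0.22 | 0.261 | 0.2610 |
| 0.26 | 0.382 | 0.3824 |
| 0.30 | 0.507 | 0.5075 |

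All six agree to three decimals. The arithmetic is right for any rule that counts patients with an event of probability ptox.

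**Step 2: apply the written rule under the printed heading.** If ptox is the probability of any related SAE, the number of patients the rule counts is Binomial(12, f × ptox), with f at most 1. The tail increases with the event probability, so the stopping probability cannot exceed the printed value and equals it only at f = 1.

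| ptox | f = 1 | f = 0.75 | f = 0.50 |
|---|---|---|---|
| 0.10 | 0.0256 | 0.0096 | 0.0022 |
| 0.14 | 0.0750 | 0.0301 | 0.0075 |
| 0.18 | 0.1552 | 0.0671 | 0.0180 |
| 0.22 | 0.2610 | 0.1216 | 0.0351 |
| 0.26 | 0.3824 | 0.1923 | 0.0597 |
| 0.30 | 0.5075 | 0.2756 | 0.0922 |

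**Step 3: patients exposed.** The futility stop has probability 0.95^12 = 0.5404 at ORR 5% and 0.75^12 = 0.0317 at ORR 25%, matching the printed 54% and 3%. Futility alone therefore allows 4 × (1 − 0.5404) = 1.84 and 4 × (1 − 0.0317) = 3.87 expected further patients. Multiplying by (1 − safety stop) at ptox 0.30, with response and SAE taken as independent and all four patients enrolled after the safety look, gives:

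| ORR | f = 1 | f = 0.75 | f = 0.50 |
|---|---|---|---|
| 5% | 0.91 | 1.33 (+0.43) | 1.67 (+0.76) |
| 25% | 1.91 | 2.81 (+0.90) | 3.52 (+1.61) |

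Figures in brackets are the excess over f = 1, computed before rounding.

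**The case against.** The table directly follows the rule and is introduced as describing it. On that reading ptox is shorthand for whatever event the rule counts, every printed value is exact, and only a word is missing from a heading. Repeating the Group 1 numbers proves nothing, since 4 of 12 gives the same binomial grid for any event. This is a fair reading, and it is why the arithmetic is not criticised. But the heading names a different event, and nothing in the section says that the rule's wording prevails over it.

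The sizes rest on assumed shares, and ptox 0.30 is the row with the largest absolute gap. Both points stand: a share of 100% leaves no gap, and at ptox 0.10 the differences are small in absolute terms. The exposure figures are also maxima for those shares. Section 5.2.2 opens the second stage on response: "If one or more of these patients respond, an additional four patients will be enrolled". It does not make those patients wait for the safety look, and patients already enrolled cannot be spared by either version of the rule.

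On the definition, section 7.1 separates the CAEPR (known and potential events) from the SPEER (reporting exceptions), so the CAEPR may seem the natural reference. That is plausible, but the plan does not say so. External NCI reporting guidelines are cited, but section 13.2.2 does not point to them for this term.

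Finally, section 5.2.2 provides for teleconferences every two weeks at which "all patient toxicities, including all serious adverse events (SAE) and all other clinical data will be reviewed". That limits the harm. It supplies neither a numerical boundary nor a meaning for *unexpected*.

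**Conclusion.** The concern holds. Section 13.2.2 states its safety rule for one event and heads its table with a broader one. Under that heading the printed stopping probabilities are upper bounds for the written rule. In the text available for review, *unexpected* is neither defined nor linked to a list.

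The size of the gap depends on a share that the documents do not give. At ptox 0.30 it is nil at 100%, 0.507 against 0.276 at 75%, and 0.507 against 0.092 at 50%. Under the stated assumptions, the two lower shares correspond to at most about 0.4 to 0.8 more expected patients at ORR 5%, and 0.9 to 1.6 more at ORR 25%.

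The practical reach is small. There is one decision rule, at most four patients remain to be enrolled (none if futility stops the group), the analysis table in section 13.2.1 has all AEs and SAEs summarised, and the efficacy error rates are untouched. It should still be fixed, because this is the group's only formal toxicity boundary and the correction is cheap.

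**What to change.** Reconcile the rule and the table heading in section 13.2.2 so that both name the same event. Which event stops accrual is for the sponsor to decide.

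- If all study-drug-related SAEs are meant, bring the rule's wording into line with the heading. The rule can then trigger more often than under the present wording.
- If only unexpected ones are meant, relabel ptox as the per-patient probability of an unexpected study-drug-related SAE, and add one line naming the reference list against which expectedness is judged.

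The six printed probabilities are correct in either case, so no further table is needed. The cost is one wording change, plus one line if *unexpected* is kept. Sample size and efficacy rules do not change.
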